##### **5.1.1 Subgroups**

Given the a priori hypothesis that treatment effect may differ according to gender or HIE severity we will conduct a pair of subgroup analyses that assesses treatment effects separately for males and for females, and separately for moderate and severe HIE. Subgroup specific treatment effects will be computed and inference will be based on a single covariate-by-treatment test for interaction using logistic regression.

#### **5.2 Secondary Outcomes**

Generalized linear regression models will be used for binary and continuous secondary outcomes, adjusted for recruitment site and HIE severity.

#### **5.3 Exploratory Outcomes**

Generalized linear regression models will be used for exploratory binary and continuous outcomes, adjusted for recruitment site and HIE severity. Regression models for ordered categorical outcomes (proportional odds models) will be used to provide treatment effect estimates adjusted for recruitment site and HIE severity. Quantitative measures include MRI-based injury score using the Washington University Standardized Scoring System. For these endpoints, differences and 95% confidence intervals in median brain MRI injury scores between groups will be assessed using bootstrapped resampling with replacement.

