1.1.3 AIM 3: Biomarkers of Neonatal Brain Injury

Aim 3a. To determine whether early high dose Epo decreases the severity of brain injury as evidenced by early neonatal MRI and MR spectroscopy.

Aim 3b. To determine whether early high dose Epo decreases the severity of brain injury as evidenced by serial circulating biomarkers of inflammation and brain injury.

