9.3 DATA ANALYSES

9.3.1 Primary outcome analyses

The primary analysis will be a test of equality of the rate of the primary outcome (death or neurodevelopmental impairment (NDI)) across the two randomized investigational groups. Specifically, we will use a likelihood ratio test based on logistic regression, with stratification by recruitment center and HIE severity. We will perform Intention to Treat analysis and expect minimal non-compliance due to the nature of the intervention in relation to in-patient care. For

the primary endpoint, we expect uniform and complete ascertainment of death but may not evaluate all subjects for developmental impairment. We plan to perform a primary analysis based on complete cases and will exclude those subjects for whom vital status is known (alive) but NDI cannot be assessed. Sensitivity analysis will use multiple imputation to evaluate the potential impact of any missing data. Secondary analysis will consider an ordered categorical two-year status measure (death/severe or moderate impairment/mild impairment/normal), and analysis will be based on generalized Wilcoxon tests or regression models for ordered categorical outcomes such as the proportional odds model. Secondary quantitative measures include MRI-based injury score using the Washington University Standardized Scoring System. For these endpoints, a stratified t-test provides inference regarding the mean response across the treatment groups. We will adjust all secondary outcome analyses for recruitment site and HIE severity using regression methods.

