## 5.8 Neuroimaging Outcomes

The primary neuroimaging outcome measures are: (1) the total injury score (derived from the HEAL/Wash U MRI scoring system above) and (2) the ratio of lactate/NAA determined for the left thalamus and parietal white matter from the quantitative MRS data. For the MRI injury score and the lactate/NAA ratio, we will use linear regression to compare Epo treated patients to controls while adjusting for site and HIE severity since these are factors used to stratify the randomization. If we have missing data due to either early patient death or other factors (e.g., family declines MRI or infant is unable to complete all the sequences), we will estimate the resultant sampling bias by comparing our final neuroimaging sample to the overall HEAL sample with regard to patient demographics and primary outcome data.

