**Table 3. Distribution of outcomes in previous studies**

	NEATO Epo (n=22)	NEATO Placebo (n=25)	Bayley III Cognitive	Trivedi et al. (submitted)
Injury Severity			Mean	Std. Dev.
None (0)	8 (36%)	3 (12%)	96	(8)
Mild (1-11)	13 (59%)	11(44%)	100	(13)
Moderate (12-32)	1 (5%)	6 (24%)	85	(18)
Severe (>32)	0 (0%)	5 (20%)	76	(19)
Predicted Bayley III (Mean (SD))	97.9 (11.7)	91.1(15.2)		
Predicted %<90	25.1%	47.1%		
Predicted death/NDI	34.1%	54.5%		

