## 7.3 Sample size for MRI/MRS biomarkers

For imaging measures, we will have data for all subjects. Assuming a 10% missing data rate we have 80% power to detect a difference in the mean of secondary outcomes across treatment groups of 0.26 SDs. For the inflammation and brain injury biomarkers, we will have a total of 200 subjects and have 80% power to detect a mean difference across the treatment groups of 0.4 SDs.

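### SAP 5.3 bases inference on the tied 0–138 MRI injury score on an unadjusted bootstrap of medians, which is insensitive to moderate and severe injury; SAP 5.8 analyses the same score differently, and neither is named as lead

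*SAP*

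**What the plan says.** Aim 3a in Protocol 1.1.3 is "To determine whether early high dose Epo decreases the severity of brain injury as evidenced by early neonatal MRI and MR spectroscopy". Three places then give an analysis of the MRI injury score:

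- SAP 5.3 (exploratory outcomes): "differences and 95% confidence intervals in median brain MRI injury scores between groups will be assessed using bootstrapped resampling with replacement". The other models in that section are stated to be adjusted for recruitment site and HIE severity. This sentence states no adjustment, no stratified resampling and no bootstrap type.
- SAP 5.8, which lists the total injury score as a primary neuroimaging measure: "we will use linear regression to compare Epo treated patients to controls while adjusting for site and HIE severity".
- Protocol 9.3.1, which lists the score among secondary quantitative measures: "a stratified t-test provides inference regarding the mean response across the treatment groups". It also promises adjustment for site and HIE severity in all secondary analyses.

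On power, SAP 7.3 starts from "Assuming a 10% missing data rate" and says "we have 80% power to detect a difference in the mean of secondary outcomes across treatment groups of 0.26 SDs". No document gives power for a comparison of medians.

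SAP 4.3 defines the score as a total from 0 to 138, banded as none (0), mild (1–11), moderate (12–32) and severe (33–138). SAP Table 3, "Distribution of outcomes in previous studies", gives the phase II band counts.

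**The concern.** The aim is about severity of injury, so the analysis should respond when infants move out of the moderate and severe bands or when injury within those bands becomes less bad. A difference in medians responds only to what happens around the middle of each arm. If the middle sits in the mild band, a real effect in the upper part of the scale can leave the medians unchanged. The score is also an integer with many ties, so the bootstrap distribution of a median is lumpy and its interval can be too wide.

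What is at stake is the MRI evidence for Aim 3a, not the primary efficacy conclusion. With two SAP analyses of one score and no stated order, the report could lead with the less sensitive one, or the choice could be made after the results are known.

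**Working it through.** **1. The plan's own power figure.** With 10% missing, 250 per arm becomes 225. For two means, two-sided 5% (stated for the four-level outcome and assumed here):

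power = Φ(δ√(n/2) − 1.96) = Φ(0.26 × √112.5 − 1.96) = Φ(2.758 − 1.960) = Φ(0.798) = 78.7%.

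The stated 80% corresponds to δ = 0.264 SD. The figure reproduces, for means.

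**2. Where the medians lie.** From SAP Table 3, 3 + 11 = 14 of 25 placebo infants and 8 + 13 = 21 of 22 Epo infants scored 11 or less. The middle placebo value is the 13th, so both medians are at most 11. With 225 placebo infants and the same 56% share, 126 are expected at or below 11 and the median is the 113th. The sample median would exceed 11 with probability of about Φ((112.5 − 126)/√(225 × 0.56 × 0.44)) = Φ(−1.81) = 3.5%. Protocol 2.2.3 reports phase II scores of 4.0 against 16.4 without naming the summary. On these counts 16.4 cannot be the placebo median, so the motivating contrast was not one of medians.

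**3. A case that needs no assumption about the median.** Suppose Epo turned every severe scan into a moderate one: placebo 12/44/24/20%, Epo 12/44/44/0%. The share at or below 11 stays at 56%, so the true median difference is zero. In simulation the percentile bootstrap flagged a difference in about 2% of trials, an unstratified rank test in 34% and a comparison of means in 100%.

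**4. Error rate and power in general.** Inputs: 225 per arm; band shares from the phase II placebo arm, or from both arms pooled (11/47 = 23.4% at zero). Assumptions not in the documents: three within-band shapes (uniform and two skewed low), 23% severe HIE, severity as the only stratum (site not simulated), and 800 resamples for the bootstrap. Rejection rates under no effect, nominal 5%:

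- percentile bootstrap: 0.6–1.9%; 3.4% when one placebo-like shape is made continuous within bands, so most of the conservatism there comes from ties
- normal-approximation bootstrap (estimate ± 1.96 bootstrap standard errors): 1.1–2.5% on placebo-like scores, 3.5–5.1% on pooled scores; a further simulation gave 1.4–7.5%
- van Elteren test: 4.5–5.8%
- adjusted linear regression: 4.1–6.1%

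Power at a mean difference of 0.26 SD of the reference distribution, produced either by moving infants toward the phase II Epo bands or by scaling scores down (three shapes per row):

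| Reference scores, effect | Percentile bootstrap | van Elteren | Gap (points) | Adjusted regression |
|---|---|---|---|---|
| Placebo-like, band shift | 75–80% | 97–99% | 19–22 | 88–91% |
| Placebo-like, scaling | 28–72% | 80–87% | 15–52 | 94–95% |
| Pooled, band shift | 31–39% | 87–89% | 49–57 | 94–95% |
| Pooled, scaling | 19–80% | 89–95% | 15–70 | 97% |

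With 700 trials per cell, the Monte Carlo standard error is at most √(0.25/700) = 1.9 points. The normal-approximation bootstrap had 34–88% power over the same settings.

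**5. Fine strata.** Stratifying by site and severity gives 17 × 2 = 34 strata (about 450/34 = 13 infants each), or 60 at the maximum of 30 sites (about 7.5 each). At 40% of the phase II shift, with strata assumed uninformative, the unstratified rank test had 95–96% power, van Elteren 92–93% (34 strata) and 89% (60 strata), and the percentile bootstrap 65–74%.

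**The case against.** The strongest reply is that the median interval is not the only inference on this score. SAP 5.8 already compares arms by linear regression adjusted for both stratification factors, with 88–97% power in the settings above. SAP 4.3 adds the four-level MRI severity classification as a secondary measure, and SAP 5.3 provides adjusted proportional-odds models for ordered outcomes, so moderate and severe injury are not ignored across the plan. The analysis is exploratory, and a median difference in score points with an interval is a legitimate, readable summary of a skewed score.

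This stands, and it limits the point. A reader might infer that a real MRI benefit would be reported only as no difference in medians. SAP 5.8 rules out so strong a claim. The reply does not settle which result leads, and it does not repair the missing adjustment or the unspecified bootstrap type in SAP 5.3.

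A second reply is that the conservatism and the power gap depend on choices the documents leave open. That is also correct: the normal-approximation form can be near nominal, and fine stratification costs the rank test a few points. In all the settings tried, however, the percentile form was conservative and less powerful than the rank test.

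**Conclusion.** The point holds in a limited form. The SAP 5.3 median bootstrap is a weak basis for inference on this score. In percentile form it rejects in about 1–2% of trials instead of 5% under no effect, and at 0.26 SD it has roughly 15–70 points less power than a rank test stratified by severity. It is nearly blind to the removal of all severe injury. The unranked coexistence of SAP 5.3 and SAP 5.8 needs no simulation to establish.

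Two further readings are tempting but unsupported:

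- A reader might infer that the trial misses its stated 80% imaging power. That figure is for means, reproduces at 78.7%, and is met by the SAP 5.8 regression in the simulations. The median bootstrap has no stated power to miss.
- A reader might want one number for the loss, such as 30 points. Gaps of 27–36 points arise for band shifts of 0.12–0.18 SD on placebo-like scores, but the documents give no within-band distribution, so only the range can be defended.

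The sizes rest on the phase II band shares, the assumed within-band shapes and share of severe HIE, and 225 evaluable infants per arm. The location of the medians and the severe-to-moderate argument rest on the band shares alone.

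**What to change.** - **SAP 5.3:** keep the median difference as a descriptive summary. If an interval is shown with it, state the bootstrap type and resample within strata. Base inference on a method that accounts for HIE severity and site: a van Elteren test, or a proportional-odds model on the score adjusted for both factors. With 34 or more site-by-severity strata van Elteren may lose a few points of power, so the proportional-odds model is a reasonable alternative.
- **SAP 5.3 and 5.8:** retain the adjusted regression of means alongside, since it detects changes at the top of the scale that a rank test sees only partly. Name one of the two as lead before scores are compared by arm, and say that this replaces the t-test in Protocol 9.3.1.
- **SAP 7.3:** state that the 0.26 SD figure refers to the comparison of means.

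The cost is a few sentences of SAP text. Proportional-odds and linear models are already in the plan, and no data collection changes. The downside is that an odds ratio or rank-based effect is less directly readable than score points; the descriptive medians and the regression estimate partly make up for that.

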## 5.4 Exploratory Prognostic Biomarkers

We will consider two main classes of potential predictors of 24-month status: neuroimaging measures and inflammatory markers. Interest is in the prognostic potential of individual and/or combined biomarker measurements. Given that the primary outcome is a binary measure (NDI), we will evaluate the predictive potential of individual quantitative measures using ROC curves showing the full potential of sensitivity and specificity across marker cut points. We will compute ROC curves for the (4) primary neuroimaging measures, and separately for individual inflammatory markers. We will derive two multivariate predictive models: using the inflammatory markers and using the MRI and MRS measures. We will use AIC and 10-fold cross-validation to develop and validate predictive models. A final multivariate model will combine markers from both MR and inflammatory measures, and 10-fold cross-validation will permit inference in the incremental value of adding markers in combination by comparing ROC curves and associated area under the ROC curve (AUC). Evaluation of whether treatment modifies the prognostic potential of biomarkers can be conducted by testing for the interaction between treatment status and individual biomarkers in predictive models for 2-year outcomes.

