6.3.5 Plasma and urine biomarkers; baseline Epo measurement

Three blood samples (1.5 mL each) will be collected in EDTA tubes from each enrolled patient over the course of their hospital stay to be used to study circulating biomarkers of inflammation and brain injury. The first blood sample (collected prior to the administration of study drug) will also be used to measure a baseline Epo level. A baseline Epo level may be helpful to determine the chronicity of hypoxic-ischemic stress *in utero*, a potential confounder of the relationship between Epo therapy and 2-year outcome. Additional samples are collected on Study Days 2 and 4.

Samples may be refrigerated for up to 4 hours prior to processing and freezing. As soon as possible after drawing, samples should be spun for 8 min at 2000 G, plasma removed into a separate container, and plasma and pellet stored in labeled tubes at -70°C or below. RNALater will be added to one pellet to preserve RNA for future studies. Please refer to the Laboratory SOP for further details. Plasma Epo concentrations will be measured in duplicate using Meso Scale Discovery (MSD) technology at the UW Laboratory Core.

We will assay blood samples for circulating biomarkers of brain injury and inflammation in a subset of infants (N = 200; 100 treated and 100 control infants with balanced numbers of moderate and severe HIE. These subjects will all have MRI scans that have met pre-defined acceptance criteria). We will assay putative biomarkers of brain injury severity in neonates including: S100B, glial fibrillary acidic protein (GFAP), Tau, neuron-specific enolase (NSE), and ubiquitin C-terminal hydrolase-L1 (UCH-L1). Given the role of inflammation in HIE, we will also measure the following inflammatory markers: interleukin (IL)-1beta (β), IL-6, IL-8, and tumor necrosis factor-alpha (TNF-α). All samples will be run in duplicate using MSD technology in the UW core laboratory. This combination of factors will allow us to evaluate the subject's inflammatory

state over time, provide insight as to the timing and severity of brain injury, and potentially, provide insight as to why some individuals might respond more optimally to Epo.¹²⁴⁻¹²⁷

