### 1.3 Randomization

Randomization sequences will be created centrally by the Data Coordinating Center (DCC). The DCC will provide each site pharmacy with a randomization look-up table that pairs each study ID with a treatment allocation. Randomization is stratified by site and HIE severity level (“moderate” vs. “severe” HIE) based on the modified Sarnat score. The site pharmacy will then draw up the assigned study drug dose into a syringe, based on the randomization list. The appearance of the syringes of Epo and placebo are identical, thus the bedside staff remain masked. Only the research pharmacist and DCC biostatistician will be un-masked to treatment assignment. All parents, study and clinical staff, as well as all Clinical Coordinating Center (CCC) members, will remain masked to treatment assignment throughout follow-up. To ensure balance within clinical centers, the randomization will be implemented using a randomly permuted blocks design to ensure approximate balanced assignments within site and HIE severity level. The sequence of assignments for each site and stratum will be prepared in advance by the DCC.

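### The exploratory prognostic analysis can show that blood and MR markers predict 24-month outcome, but not whether they add anything to the HIE severity grade known at entry

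*SAP*

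**What the plan says.** SAP 5.4 limits the candidate predictors to two kinds: "We will consider two main classes of potential predictors of 24-month status: neuroimaging measures and inflammatory markers". It then sets out three steps.

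- Single markers: "We will compute ROC curves for the (4) primary neuroimaging measures, and separately for individual inflammatory markers".
- Models by marker class: "We will derive two multivariate predictive models: using the inflammatory markers and using the MRI and MRS measures".
- A combined model: "A final multivariate model will combine markers from both MR and inflammatory measures". Added value is assessed at this step: "10-fold cross-validation will permit inference in the incremental value of adding markers in combination by comparing ROC curves".

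The only variable named that is not a marker is treatment, through possible "testing for the interaction between treatment status and individual biomarkers in predictive models for 2-year outcomes". Protocol 9.3.3 gives the same plan.

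Severity is available throughout. Protocol 6.3.2.1 requires the Sarnat items to be entered in the portal before an infant can be randomised, and the portal calculates the grade. SAP 1.3 states: "Randomization is stratified by site and HIE severity level". The SAP adjusts for severity in the primary (5.1), secondary (5.2), exploratory-outcome (5.3), safety (5.5), circulating-biomarker (5.7) and neuroimaging (5.8) analyses. All of these compare treatment arms, and nothing carries the adjustment over to 5.4.

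On the assay subset, Protocol 6.3.5 describes "100 treated and 100 control infants with balanced numbers of moderate and severe HIE". Protocol 9.3.5 and SAP 5.7 instead describe a randomly selected subset of 200, and mention both severity grades only by way of example.

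**The concern.** Endpoint 6 in Protocol 1.2 concerns how well early markers predict 24-month outcome. A clinician reading the result will want to know whether the assay or scan tells them more than the examination already done. Protocol 6.3.5 itself presents the brain-injury assays as candidate markers of injury severity, so some overlap with the Sarnat grade is to be expected. A marker that tracks the grade and carries nothing else would still have an AUC above 0.5, and the planned models give no way to tell it from a marker with independent information. Cross-validation does not help, because it guards against overfitting and a severity proxy predicts just as well in held-out folds.

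The arms raise a related point. The models pool infants whose assumed outcome rates are 49% and 33%. The baseline blood sample precedes dosing, but the Day 2 and Day 4 samples and the MRI follow it. If Epo shifts a marker, part of that marker's association with outcome comes through arm.

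**Working it through.** SAP 5.4 states no AUC, power or sample size, so there is no figure of the plan's own to reproduce. What follows is an illustration.

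**Inputs from the documents.** Outcome rates of 49% (control) and 33% (Epo), SAP 7.1; with equal arms the pooled rate is P = (0.49 + 0.33)/2 = 0.41. Assay subset of 200; 450 evaluable infants.

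**Assumed, because the documents do not give them.** Severe share s = 20% to 50%; severe-minus-moderate risk difference r = 20 to 40 points; marker N(0,1) in moderate and N(d,1) in severe infants, d = 1 to 2 SD, with no link to outcome once severity is known.

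**Formulas.** Let Δ be the severe share among events minus the severe share among non-events. Then Δ = s(1−s)r / [P(1−P)], with P(1−P) = 0.41 × 0.59 = 0.2419.
- AUC of severity alone = 0.5 + Δ/2.
- AUC of the severity-only marker = 0.5 + Δ × [Φ(d/√2) − 0.5]. The bracket is 0.260, 0.356 and 0.421 for d = 1, 1.5 and 2.

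**Results.**

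| s | r | Δ | AUC, severity | AUC, marker (d = 1 to 2) |
|---|---|---|---|---|
| 0.20 | 0.20 | 0.16×0.20/0.2419 = 0.132 | 0.57 | 0.53 to 0.56 |
| 0.30 | 0.30 | 0.21×0.30/0.2419 = 0.260 | 0.63 | 0.57 to 0.61 |
| 0.50 | 0.40 | 0.25×0.40/0.2419 = 0.413 | 0.71 | 0.61 to 0.67 |

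So a marker with nothing beyond severity shows a crude AUC of about 0.53 to 0.67.

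**With and without severity in the model.** Logistic models were fitted to 1,000 simulated data sets per case, with d = 1.5 and (s, r) = (0.5, 0.4), (0.3, 0.3) and (0.2, 0.4). The likelihood ratio test for the marker was significant at 5% in 62% to 95% of data sets of 200 without severity, and in 92% to 100% of data sets of 450. With severity in the model it was significant in 4% to 6% at both sizes. The two tests ask different questions: the first is power for a real crude association, the second tests for added value.

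**Arm.** The same formula with half the infants in each arm and a 16-point difference gives Δ = 0.25×0.16/0.2419 = 0.165, so arm alone has AUC 0.58. For a marker shifted between arms by 0.4 SD (the difference SAP 7.3 is powered for) and unrelated to outcome within arm, the bracket is 0.111 and the AUC is 0.5 + 0.165×0.111 = 0.52. On these inputs, pooling arms matters less than omitting severity.

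**If the assay subset were 50:50 by severity.** Take s = 0.30, r = 0.30: risks are 0.41 − 0.09 = 0.32 (moderate) and 0.62 (severe). In a 50:50 subset P = 0.47, Δ = 0.25×0.30/(0.47×0.53) = 0.301, and the d = 1.5 marker moves from 0.593 to 0.607. With s = 0.20, r = 0.40 (risks 0.33 and 0.73), P = 0.53, Δ = 0.25×0.40/(0.53×0.47) = 0.401, and it moves from 0.594 to 0.643. Such a subset needs 100 severe infants: 20% of 500 is exactly 100, and 15% is only 75.

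**The case against.** The strongest reply is that the plan answers the question it poses. SAP 5.4 and Endpoint 6 speak of the markers' predictive potential and claim nothing beyond the Sarnat grade. A marker that tracks severity does predict outcome, and reporting so is correct. That stands. What it leaves open is added value over a clinical baseline, which the plan evaluates only between marker sets.

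A reader might infer that the 62% to 95% figures are false-positive rates. They are not: in the crude sense the association is real, and SAP 5.4 names no test of a single-marker AUC against 0.5.

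A reader might also infer that the assay subset is deliberately enriched to half severe, which would inflate all the AUCs. The documents do not support that. The wording in Protocol 6.3.5 could mean balance between arms, Protocol 9.3.5 and SAP 5.7 describe a random subset, and a 50:50 split is not achievable if only 15% of infants are severe. Enrichment would in any case not touch the MR-only curves and model, since imaging is planned for all infants.

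Finally, the analysis is exploratory and severity is already recorded, so the extra model could be run later without new data. That limits the weight of the point, but specifying the model in advance costs almost nothing.

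**Conclusion.** The point holds as a limit on what the prognostic analysis can conclude, and as a cheap improvement. It is not an error in the crude ROC curves. As written, Endpoint 6 can be answered for crude prediction but not for information beyond the entry severity grade. The primary, secondary and safety results do not depend on it.

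The omission is plain in both documents. Its numerical effect is not fixed by them: the AUC range of 0.53 to 0.67 rests on assumed severe shares, risk differences and marker shifts, and at the low end (20% severe, 20-point difference) the effect is small. Any effect of assay-subset selection is conditional on a reading that the documents leave unresolved.

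**What to change.** In SAP 5.4 and Protocol 9.3.3:

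1. Keep the single-marker ROC curves, labelled as crude description.
2. Add a base model with HIE severity and treatment arm.
3. Report the change in cross-validated AUC when the inflammatory, MR and combined marker sets are each added to the base model, with a likelihood ratio test. Run the test on the pre-specified marker sets rather than on sets chosen by AIC, and repeat any AIC selection inside each fold.
4. Show ROC curves separately within moderate and severe HIE.

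Separately, reconcile Protocol 6.3.5 with Protocol 9.3.5 and SAP 5.7 on how the 200 infants are chosen. Only if the subset is deliberately enriched for severe HIE should the blood-marker AUCs be weighted back to the enrolled severity mix.

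The cost is wording and two variables already recorded. Marker contributions will look smaller, and the curves within the smaller severity stratum will be less precise.
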